### INSTRUCTIONS:

#### ANCILLARY REVIEWS

Which ancillary reviews do I need and when do I need them? Refer to HRP-309 for more information about these ancillary reviews.			
Select yes or no	Does your study...	If yes...	Impact on IRB Review
 Yes  No	Include Gillette resources, staff or locations	Gillette Scientific review and Gillette Research Administration approval is required. Contact: [contact]	Required prior to IRB submission
 Yes  No	Involve Epic, or Fairview patients, staff, locations, or resources?	The Fairview ancillary review will be assigned to your study by IRB staff Contact: [contact]	Approval must be received prior to IRB committee/designated review.
 Yes  No	Include evaluation of drugs, devices, biologics, tobacco, or dietary supplements or data subject to FDA inspection?	The regulatory ancillary review will be assigned to your study by IRB staff Contact: [contact]  See: https://policy.umn.edu/research/indide	Consider seeking approval prior to IRB submission.
 Yes  No	Require Scientific Review? Not sure? See guidance on next page.	Documentation of scientific merit must be provided. Contact: [contact]	
 Yes  No	Relate to cancer patients, cancer treatments, cancer screening/prevention, or tobacco?	Complete the CPRC application process. Contact: [contact]	

## MEDICAL PROTOCOL (HRP-590)

PROTOCOL TITLE: Magnesium sulfate as adjuvant analgesia and its effect on opiate use by post-operative transplant patients in the pediatric ICU.

VERSION DATE: 06/09/2022

 Yes  No	Include the use of radiation? (x-ray imaging, radiopharmaceuticals, external beam or brachytherapy)	Complete the AURPC Human Use Application and follow instructions on the form for submission to the AURPC committee. Contact: [contact]	Approval from these committees must be received prior to IRB approval;  These groups each have their own application process.
 Yes  No	Use the Center for Magnetic Resonance Research (CMRR) as a study location?	Complete the CMRR pre-IRB ancillary review Contact: [contact]	
 Yes  No	Include the use of recombinant or synthetic nucleic acids, toxins, or infectious agents?	Complete the IBC application via eprotocol.umn.edu Contact:	
 Yes  No	Include the use of human fetal tissue, human embryos, or embryonic stem cells?	Contact OBAO for submission instructions and guidance	
 Yes  No	Include PHI or are you requesting a HIPAA waiver?	If yes, HIPCO will conduct a review of this protocol. Contact: [contact]	
 Yes  No	Use data from the Information Exchange (IE)?	The Information Exchange ancillary review will be assigned to your study by IRB staff Contact: [contact]	Approval must be received prior to IRB approval.  These groups do not have a separate application process but additional
 Yes  No	Use the Biorepository and Laboratory Services to collect tissue for research?	The BLS ancillary review will be assigned to your study by IRB staff. Contact: [contact]	

**REVISION HISTORY**

Revision #	Version Date	Summary of Changes	Consent Change?
1	2/15/2020	Clarify blood draw spacing if infusion turned off, clarify COVID influence on patient enrollment and consent procedure, minor adjustments to data build	No
2	12/15/2021	Updated co-investigator status and IDS#, updated timing of MgSO4 initiation in liver transplants (4.1), eliminated need for dose conversion calculations – pump library was fixed (13.1), deleted method for MME calculation with identification of relevant literature (15.1)	No
3	04/12/2021	Updated version date, minor formatting corrections (8.1,8.2), added new exclusion criteria (8.2), added new withdrawal criteria clarifier (12.1), increased language regarding potential for less patient enrollment (10.1), added risk of protocol deviation (13.1), added additional monitoring element to prevent protocol deviation (18.1)	No
4	6/9/2021	Provided additional wording responding to stipulation letter for continued magnesium approval (18.1)	No

MEDICAL PROTOCOL (HRP-590)

PROTOCOL TITLE: Magnesium sulfate as adjuvant analgesia and its effect on opiate use by post-operative transplant patients in the pediatric ICU.

VERSION DATE: 06/09/2022

## MEDICAL PROTOCOL (HRP-590)

PROTOCOL TITLE: Magnesium sulfate as adjuvant analgesia and its effect on opiate use by post-operative transplant patients in the pediatric ICU.

VERSION DATE: 06/09/2022

## MEDICAL PROTOCOL (HRP-590)

PROTOCOL TITLE: Magnesium sulfate as adjuvant analgesia and its effect on opiate use by post-operative transplant patients in the pediatric ICU.

VERSION DATE: 06/09/2022

### ABBREVIATIONS/DEFINITIONS

Include any abbreviations or definitions for key or technical terms you use in your protocol.

- PICU: pediatric intensive care unit
- TPIAT: total pancreatectomy and islet cell autotransplantation
- CTSI: Clinical and Translational Science Institute
- BPIC: Best Practices Integrated Informatics Core
- IDS: investigational drug service
- IND: investigational drug
- FDA: Food and Drug Administration
- UMN: University of Minnesota
- PI: principal investigator
- EMR: electronic medical record
- MgSO4: magnesium sulfate
- PCA: patient-controlled analgesia (machines where patient can press button to have medicine delivered, giving them more personalized control of their care)
- POD#0: post-operative day #
- OR: operating room
- T&A: tonsillectomy and adenoidectomy
- IV: intravenous
- pt: patient
- PO: per os (latin for 'by mouth')
- PRN: pro re nata (latin for 'as needed')
- mg: milligram
- kg: kilogram
- hr: hour
- AE: adverse event
- SAE: serious adverse event
- CRF: case report form
- PACCT: Pediatric Pain and Advanced/Complex Care Team
- CRNA: certified registered nurse anesthetist

## MEDICAL PROTOCOL (HRP-590)

PROTOCOL TITLE: Magnesium sulfate as adjuvant analgesia and its effect on opiate use by post-operative transplant patients in the pediatric ICU.

VERSION DATE: 06/09/2022

### 1. Objectives

- 1.1. Purpose: To use magnesium sulfate as adjuvant analgesia by implementing a treatment protocol in order to determine whether it can benefit pediatric pain in post-operative transplanted patients and decrease overall opioid consumption.

### 2. Background

- 2.1. Significance of Research Question/Purpose: Our study's purpose would be to improve analgesia in TPIAT (total pancreatectomy and islet cell autotransplant) and liver transplant recipients in the PICU, and to expand growing literature regarding magnesium as an analgesic, including in a yet-studied population. There is currently some promising data that MgSO4 can be beneficial as an analgesic in certain operative and post-operative pediatric patients, though data remains mixed depending on the method of magnesium delivery, as well as the dosing used and study design. Pain remains a significant source for morbidity in post-transplant pediatric patients, and to our knowledge use of magnesium for analgesia has not been studied in these populations. Opioid-sparing medication and targeting new analgesic options is an important and growing research topic in medicine.
- 2.2. Preliminary Data: To our knowledge there is no data regarding magnesium use for pain control in post-operative transplant patients, despite growing literature of effective use of magnesium as an analgesic (both adults and pediatrics). There is data in MgSO4 pediatric analgesia studies, extrapolated data from continuous MgSO4 infusions in asthmatics, and numerous adult studies, the combination of which support safety for our intended infusion dosing in our study.
- 2.3. Existing Literature: Early data regarding MgSO4 use as adjuvant analgesia dates back to the late 90's in adult literature (2), and has since been studied in a wide variety of those populations, with some meta-analysis data now showing efficacy as well (3-13). Pediatric literature often lags behind, however now also has growing data over the past two decades. Much of the pediatric analgesic-specific data is in tonsillectomy populations, which has mixed but promising results on efficacy depending on the method of delivery as well as outcome measure studied (14,15,22-25,28-29). Potentially more comparable pediatric populations to our proposed study population include osteotomies in cerebral palsy and scoliosis repairs, which both tend to have more analgesic requirement than T&A. Both of these populations have been studied and shown to have decreased opioid needs and/or pain scores with magnesium analgesia (17,18). Most statistically significant beneficial data of MgSO4 use cites a bolus IV dose in the OR, followed by a continuous infusion during the procedure. Adult studies have shown potential benefit in extending this infusion beyond the OR as well (40,41). Given the increased and prolonged opioid needs in the PICU course of both liver

## MEDICAL PROTOCOL (HRP-590)

PROTOCOL TITLE: Magnesium sulfate as adjuvant analgesia and its effect on opiate use by post-operative transplant patients in the pediatric ICU.

VERSION DATE: 06/09/2022

transplant and particularly TPIAT patients, we intend to implement a combination of intra-operative and post-operative magnesium protocol. To our knowledge there is no definitive therapeutic window for magnesium's analgesic effect, and studies vary as to what supra-physiologic levels are obtained based on their derived infusion protocol. Comparable intra-operative infusion doses in pediatric analgesic studies range from as low as 30 mg/kg + 10 mg/kg/hr (25) and 50 mg/kg + 8 mg/kg/hr (17) to as high as 50 mg/kg + 15 mg/kg/hr (18). The study at our proposed dosing had levels of 3.2 mg/dL immediately post-op (18). Infusions of higher doses have been used safely in pediatric asthma studies, including doses of 50-75 mg/kg + 40 mg/kg/hr for 4 hours, reaching interquartile levels of high 3's to mid 4's mg/dL (37). In adult studies prolonged infusions have been used for subarachnoid hemorrhage targeting higher ranges of 4-6 mg/dL for up to 10 days duration (38,39). Adult studies have also demonstrated efficacy in infusion protocols beyond the operative period (40,41). One protocol of 30 mg/kg + 10 mg/kg/hr was used for 48 hours in thoracotomy patients with levels of 2.8 +/- 0.3 mg/dL at conclusion (41). Prolonged infusions in pediatrics beyond 24 hrs in the literature to our knowledge exist only in asthma studies, including one with average duration of ~4 days (42). None of the above studies encountered any clinically significant magnesium side effects, and only transient diplopia and muscle weakness was reported in the adult subarachnoid hemorrhagic study when levels reached 6 mg/dL (symptoms resolved with lowering dose).

According to DynaMED and Micromedex searches on magnesium, normal levels may range 1.5 - 2.5 mEq/L (equivalent to 1.8-3.1 mg/dL), and toxic hypermagnesemic levels are typically not seen until >4 mEq/L (4.86 mg/dL), which does not yet include many of the hemodynamic and EKG changes (typically at >5 mEq/L or 6.08 mg/dL). Most background data in our referenced sources cite ~4.5-5 mg/dL as potential sources of clinically relevant magnesium toxicity. We intend to target levels well below this and will avoid adverse effects by checking serial magnesium levels and titrating our infusion dose down if needed. Level checks and titration plan is determined from existing pharmacokinetic/pharmacodynamic data, discussions with our pharmacy team, which is standardly involved with safety modifications of all admitted PICU patients, and recommendations from the FDA during the IND process. The significance and rationale for this study has been alluded to above, namely due to the extensive pain that post-operative transplant children endure, and our clinical duty to treat this medical problem (benevolence). Our post-operative patients are scheduled on a number of analgesic modalities simultaneously, including acetaminophen, NSAIDs, opioids, ketamine, non-pharmacologic intervention (child life, music therapy, etc), and even procedural (paravertebral block in TPIAT patients) - stressing both the difficulty of their pain control as well as the need for safe alternatives. Additionally, the growing threat of the opioid crisis and shortage has emphasized the need for adjuvant analgesic options in a multitude

## MEDICAL PROTOCOL (HRP-590)

PROTOCOL TITLE: Magnesium sulfate as adjuvant analgesia and its effect on opiate use by post-operative transplant patients in the pediatric ICU.

VERSION DATE: 06/09/2022

of patient populations to better distribute what opioids are available (justice). Magnesium is one of the potential adjuvants that we hope to expand existing literature on by investigating a yet-studied population. Secondary benefit from the use of MgSO4 is the optimization of hypomagnesemia, which is especially common in ICU populations, including post-transplant patients who are often on tacrolimus for immunosuppression (43-45). Hypomagnesemia in itself is associated with hypokalemia, hypocalcemia, hypoalbuminemia, metabolic alkalosis, and prolonged PICU stays (45). Based on its safety profile outlined above, promising literature search, and optimal patient population (high analgesic requirement), we feel that this study has tremendous potential for scientific significance in pediatric patients.

### 3. Study Endpoints/Events/Outcomes

- 3.1. Primary Endpoint/Event/Outcome: Primary outcome focuses on the total opioid requirement (morphine equivalent per body weight) over the operative and post-operative PICU course (which may range upwards of 7 days in some transplant cohorts). The hypothesis is that magnesium sulfate use will decrease this dosage compared to controls, however measurements will be used to determine whether the intervention does not have any statistical difference as well (or even increases doses, which would be otherwise unexpected in the literature). We intend to pilot 30 prospective transplant patients (liver, TPIAT). Retrospective control data will consist of the last 60 transplants (30 liver, 30 TPIAT), which was determined based on original power analysis targets for a larger-based study anticipated in the future. The study will be stopped prematurely if during obligated data reviews it is determined that opioid needs are increasing. The study will also be halted if 2 patients develop clinically significant adverse reactions secondary to magnesium, at minimum until able to further review dosing and protocols. If arrhythmia (other than transient bradycardia), respiratory failure, or coma are encountered once (also deemed secondary to magnesium), the study will be halted immediately with that patient. Per above, if encountering more frequent anemia than typical post-transplant, the study will be halted to evaluate lab frequency's effect. The study will also be halted for further review if there is a dosing error. A list of data measures is provided in a secondary attachment with this protocol.
- 3.2. Secondary Endpoint(s)/Event(s)/Outcome(s): Secondary outcome data will evaluate total opioid use by post-operative day (i.e. POD#1, POD#2, POD#3, etc) to help determine any variance in effect based on proximity to the surgery as well. Secondary outcomes will also focus on other opioid variables, including amount of 'requested' (PRN) opioids versus what is scheduled. Secondary outcomes will also include opioid side effect data, since these would hypothetically be less if MgSO4 does indeed lessen opioid needs. We will collect 'pain scores' as well, however literature suggests these are often difficult to

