#### 5.2. Study Procedures:

Experimental Group: There will be no operative procedures per study parameters (though the transplantation procedure itself as well as any secondary procedures from complications are otherwise per standard of care). Patient's medical record will be reviewed for basic eligibility criteria (history of myasthenia gravis or heart block). If female and of reproductive age, patient will have a urine B-hCG, which is routine prior to any abdominal surgery. The only prospective study procedure will be the magnesium protocol previously outlined, where IV MgSO4 will be delivered as a 30-minute bolus dose of 50 mg/kg (maximum 2 grams) in OR followed by a 15 mg/kg/hr infusion initiated immediately after (i.e. in OR as well) until conclusion of PICU stay or 48 hours, whichever comes first. Magnesium levels will be monitored throughout the duration of the infusion per above - every 2 hours in OR starting after bolus dose, then every 4 hours [expected window +/- 1 hour]. There are no other baseline visits or follow-up visits independent of the PICU stay and initial consent process. We do not anticipate this study intervention impacting workflow significantly, as infusion medications are standard interventions in the PICU, and these patients already have frequent blood draws. A study schedule with these interventions will be created via OnCore program to ensure compliance with protocol. Data outcomes will be collected from epic EMR at the conclusion of each patient's ICU admission by co-investigator and medical student researcher and stored in REDCap. All collected data is via EMR, so no surveys/scripts/forms are needed for data collection. Specifically, the EMR will be accessed for appropriate transplant patient, followed by selecting the appropriate surgical encounter (which would be current), followed by selecting only specific portals in Epic EMR where intended data elements are located (for example: Intake/Output section, or results review -> magnesium level, etc). Only specific data collection pathways will be targeted while in a patient's medical chart. There are no other drugs/devices involved in study or that would alter MgSO4 delivery. Similarly, there are no out-of-hospital prescriptions or interference during the ICU admission which would alter the study protocol. Any out-of-hospital contact (i.e. pre-admission consent if performed) will include adherence to COVID precautions per hospital guidelines.

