## MEDICAL PROTOCOL (HRP-590)

PROTOCOL TITLE: Magnesium sulfate as adjuvant analgesia and its effect on opiate use by post-operative transplant patients in the pediatric ICU.

VERSION DATE: 06/09/2022

Control Group: For collection of control data, a MRN list of the most recent 60 transplant patients under the same surgeon at this institution (30 liver, 30 TPIAT) who have not opted out of research will be obtained via UMN's Best Practices Integrated Informatics Core (BPIC), followed by access to EPIC EMR outside of the Information Exchange to review patient's chart and collect for intended outcomes, which are also uploaded into RedCap. This will be done in identical manner as that for prospective data collection — the EMR will be accessed for appropriate patient by MRN, followed by selecting the appropriate surgical encounter by date, followed by selecting only specific portals in epic where intended data elements are located (for example: Intake/Output section, or results review -> magnesium level, etc). Collection of this data will be initiated at the start of IRB approval and ongoing to completion. Full data analysis will be completed at conclusion of study followed by construction of manuscript. Of note, hypomagnesemia is corrected per standard ICU care with IV MgSO4 regardless of study, and liver transplant patients currently have a pre-designed magnesium replacement protocol (also used in our CVICU post-operative cardiac patients). This will still be included in data collection without adjustment to any comparison data in statistical analysis. This replacement protocol will not be used in our study as we will already be providing continuous IV MgSO4. Similarly, magnesium blood levels are checked independent of this study, although will be more frequent now for safety monitoring. These blood levels are drawn through a central line that is already in place independent of this study, so will not require percutaneous needle stick. There are no other drugs/devices involved in study or that would alter MgSO4 delivery.

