### ***SECONDARY OUTCOMES***

#### opioid variables

1. Morphine Equivalent daily variance (daily dose/kg on each post-op day)
2. Total days on IV opioids
  - will use post-operative day when IV opioid discontinued (i.e. POD#6)
3. Total days on any opioid
4. PCA variables
  - # of demands, # of deliveries (daily and total values)
  - # of escalations in infusion dose
5. Scheduled vs PRN dosing
  - scheduled dosing includes PCA infusion dose and scheduled IV or PO opioids
  - PRN includes PCA delivered doses and PRN opioids delivered

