## MEDICAL PROTOCOL (HRP-590)

PROTOCOL TITLE: Magnesium sulfate as adjuvant analgesia and its effect on opiate use by post-operative transplant patients in the pediatric ICU.

VERSION DATE: 06/09/2022

outcomes (total days on IV opioids, number of PCA demands and deliveries, number of infusion dose escalations, number of ileus events, days until first stool, emesis counts, number of days naloxone infusion required, PICU duration, number of days intubated, paravertebral block dose increases), categorical outcomes (ketamine use, presence of side effects), and continuous outcomes (FLACC, Pain Score). Longitudinal measurements of magnesium, other analgesics, ionized calcium, PTH, and creatinine levels will be analyzed using mixed effects models. Group summaries including means, standard deviations, and rates will be reported and group differences will be summarized as incidence rate ratios, odds ratios, or mean differences with 95% confidence intervals. Analyses will be conducted using the intent-to-treat principle; control group participants who underwent magnesium replacement (for hypomagnesemia or pre-designed post-transplant protocol) will be included in the control group, and experimental group participants with discontinuation of magnesium, if any, will be included in the experimental group. A two-sided 5% level result will be regarded as significant. Statistical analysis will be per statistician's updated STATISTICAL ANALYSIS SOFTWARE (also used in a previous pain study with TPIAT cohort).

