### *15.4. Data Integrity:*

Data collection is the responsibility of the clinical study staff at the site under the supervision of the site PI. The investigator is responsible for ensuring the accuracy, completeness, legibility, and timeliness of the data reported.

Source data are all information, original records of clinical findings, observations, or other activities in a clinical trial necessary for the reconstruction and evaluation of the study. All paper data (which would include only consent/assent forms) will be kept in a dedicated, locked, research space, in co-investigator's office at UMN Children's Hospital. Other source data will be stored in EPIC. Consent and assent forms will be transitioned to the patient chart upon completion. Paper copies of these forms will be stored in a locked storage bin in co-investigator's office at UMN Children's Hospital.

Protocol with study schedule and patient enrollment will be tracked with OnCore programming. Electronic data collected from the PICU admission will be stored on REDCap program as a clinical database, a secure environment delivered by the Center of Excellence for HIPAA Data intended for storing, sharing and accessing sensitive and private highly restricted files.

Data access will be limited to research assistant, research coordinator, statistician support, and key study personnel (PI and co-investigators).

Upon completion of project, the master data matrix and patient identification key will be destroyed.

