## **18. Provisions to Monitor the Data to Ensure the Safety of Participants**

## MEDICAL PROTOCOL (HRP-590)

PROTOCOL TITLE: Magnesium sulfate as adjuvant analgesia and its effect on opiate use by post-operative transplant patients in the pediatric ICU.

VERSION DATE: 06/09/2022

*18.1. Data Integrity Monitoring:* The PI and co-investigators will be in direct day-to-day contact (specifics below) throughout the study intervention and with any of the following that arise. The PI and/or co-investigator will have direct notifications any time a transplantation surgery is planned and will confirm that study intervention has been ordered correctly in medical chart on day of PICU admission. Surgery, anesthesia, ICU, and safety monitoring teams will be notified prior to interventions when a patient is confirmed as a study participant. Medical staff will be instructed to page PI and/or co-investigators as well as research coordinator in case of any intervention side effect for further direction. The PI and co-investigators are the most appropriate direct monitors, as both have full understanding of research protocol, and are also frequently in PICU with direct care of these patients. In cases where the PI or co-investigators are not present, deferral will be made to the medical team, which is already adept and required to be following lab results and ensuring nurse orders are carried out. A co-investigator will also otherwise make routine daily lab surveillance for added layer of monitoring. This level of monitoring appears appropriate as once the intervention is ordered in our EMS, nurses carry out the order throughout duration of study. There is no blinding required in this study as all participants will be intended to receive intervention, so there appears no opportunity for bias introduced by the PI or co-investigators while caring for these patients. As patients complete their ICU and conclude their involvement in study, chart reviewer will be notified to update data into REDCap. This will be further overseen by PI and co-investigators. All data collected through chart review will be collected with a standardized data collection form to ensure uniformity.

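### Opioid dose is to be compared by post-operative day, but collection stops with the PICU stay and no rule covers days after transfer, so comparisons after about POD 2 are at risk of selection by discharge

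*Combined protocol and SAP*

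**What the plan says.** Section 3.2 introduces the daily outcome ("Secondary outcome data will evaluate total opioid use by post-operative day (i.e. POD#1, POD#2, POD#3, etc") as a way to see whether the effect varies with closeness to surgery. The data list in 15.1 defines it as "Morphine Equivalent daily variance (daily dose/kg on each post-op day" and names no last day. Days run from 7am to 7am.

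Collection is tied to the PICU stay. Section 5.2 says "Data outcomes will be collected from epic EMR at the conclusion of each patient's ICU admission" and adds "There are no other baseline visits or follow-up visits independent of the PICU stay and initial consent process". Section 18.1 says "As patients complete their ICU and conclude their involvement in study, chart reviewer will be notified to update data into REDCap". For the historical controls, 5.2 says "This will be done in identical manner as that for prospective data collection". Section 15.4 describes the database in the same terms: "Electronic data collected from the PICU admission will be stored on REDCap program as a clinical database".

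Stay length is not fixed. Section 5.3 says it varies between patients, and 15.1 lists PICU duration as an outcome. Section 4.1 does not expect any child to leave before 48 hours.

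On analysis, 15.3 says "Longitudinal measurements of magnesium, other analgesics, ionized calcium, PTH, and creatinine levels will be analyzed using mixed effects models". Daily opioid dose is not named there, nor in the lists of count, categorical and continuous outcomes.

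**The concern.** If the collection plan is followed as written, a child supplies a dose for POD k only while still in the PICU. Each later day then compares whoever is left in one group with whoever is left in the other, and leaving is a post-treatment event. If children with greater opioid need stay longer, and one group leaves sooner, the group that leaves sooner is reduced faster to its high-need members.

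The plan gives three reasons why discharge might differ between groups:

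- **Treatment.** Section 2.3 links low magnesium to longer PICU stays and presents its correction as a side benefit of the drug.
- **Era.** Controls come from an earlier period, and 5.3 and 10.1 describe COVID disruption during the study.
- **Transplant mix.** Section 5.1 leaves the prospective liver/TPIAT mix unbalanced, while the controls are 30 and 30.

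At stake is the time pattern itself. A benefit that seems to fade or reverse after the first days could come from discharge alone, and so could a benefit that seems to persist.

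**Working it through.** **1. The plan's own figure.** No design figure exists for the daily outcome. The only calculation is in 15.2, for the 7-day total: SD 8.3 mg/kg, overall mean 15.5 mg/kg. A two-sample t-test with 90 per group, two-sided 5%, gives 80% power for 3.49 mg/kg, as tabulated. As a share of the control mean this is 3.49/(15.5 + 3.49/2) = 20.2%, matching the stated 20%. That is the yardstick below.

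**2. A closed form for the selection effect.** From the document: coefficient of variation 8.3/15.5 = 0.535, applied here to daily dose. Assumed, because the documents give no daily doses or discharge times: control stay normal with mean 6 and SD 2 days; log-normal dose; correlation ρ = 0.5 between need and stay; treated mean stay 5 days; no opioid effect.

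Log-scale SD: s = √ln(1 + 0.535²) = 0.502, so ρs = 0.251. With mean stay μ, the mean dose among children still present on day k, relative to the mean of all children, is

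m(μ, k) = Φ((μ − k)/2 + ρs) / Φ((μ − k)/2).

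| POD | Present, control | Present, treated | m(6, k) | m(5, k) | Ratio, treated to control |
|---|---|---|---|---|---|
| 4 | 84% | 69% | 1.063 | 1.119 | 1.05 |
| 5 | 69% | 50% | 1.119 | 1.198 | 1.07 |
| 6 | 50% | 31% | 1.198 | 1.302 | 1.09 |
| 7 | 31% | 16% | 1.302 | 1.430 | 1.10 |

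A drug with no effect on dose would appear to raise it by about 5% to 10%. A true 20% reduction would read as 1 − 0.80 × 1.071 = 14% on POD 5 and 1 − 0.80 × 1.087 = 13% on POD 6.

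**3. Sensitivity.**
- Equal stays and no effect, any ρ: bias 0.
- ρ = 0, any difference in stay: bias 0.
- One day shorter, POD 6: 5% at ρ = 0.3 and 12% at ρ = 0.7.
- Half a day shorter, ρ = 0.3, POD 6: 2.5%.
- Treated stay one day longer, ρ = 0.5: the sign reverses. On POD 6 the ratio is m(7, 6)/m(6, 6) = 1.119/1.198 = 0.93, a false 7% decrease.

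**4. A second model that respects 4.1.** This simulation allows no discharge before the end of POD 3. Daily need is log-normal with between-child SD 0.5 on the log scale, and the true reduction is 20%. The reduction seen among those still present is:

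| Discharge | POD 5 | POD 7 |
|---|---|---|
| Unrelated to dose | 20% | 20% |
| Moderately related | 18% | 17% |
| Strongly related | 16% | 13% |
| Strongly related, and quicker in the magnesium era | 10% | 4% |

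The middle two rows need no era difference, because the drug's own effect on dose shifts discharge. With no true effect and strongly dose-related discharge, the result is about 0% under equal practice, a false 6% to 10% increase if the magnesium era discharges sooner, and a false 5% to 9% decrease if later. POD 2 and POD 3 are unbiased throughout.

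**5. Counting post-transfer days as zero.** In the strongly related case, a true 20% reduction would read as 34% on POD 5 and 47% on POD 7. This is further from the truth than the selected comparison.

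**6. Precision.** If half of each group has left (15 versus 30, assumed), the standard error rises by √(1/15 + 1/30)/√(1/30 + 1/60) = 1.41. The difference detectable with 80% power goes from 0.63 to 0.91 SD.

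**The case against.** A reader might infer that the plan restricts the daily comparison to children in the PICU and that the result is therefore biased. The documents support neither statement in that form. No section defines the daily analysis set. Section 15.1 lists an undefined overall course beside the OR and PICU totals, and a count of days on any opioid, either of which could run past transfer. The sentence in 15.4 describes storage, not analysis. Bias also needs discharge to be related to opioid need, together with a group difference in discharge or a true effect acting on it. These points stand, and they limit the claim to a risk.

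Larger effects can be produced by assuming a two-day difference in stay, but that model sends Φ(−1) = 16% of treated children out before day 2, against 4.1. Even the one-day shift sends Φ(−1.5) = 7% out, so its early-day values should not be relied on. The second model avoids this.

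Section 15.3 adjusts for transplant type, age and gender and extends similar approaches to secondary outcomes. That would remove the part of the selection that runs through transplant type, but not selection by need within type.

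The bias is also small beside the noise. On POD 6 in the one-day case about 9 treated children and 30 controls remain, so the relative standard error is roughly 0.535 × √(1/9 + 1/30) = 20%, against a bias of 9%. This tempers the consequence for one day's test. It does not help the reading of a pattern that drifts the same way over several days.

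Finally, it cannot be said that the plan intends a separate test per day. The reference to other analgesics in 15.3 might be read to include opioids, although 3.2 lists other analgesic dosing apart from the opioid variables. The model for daily opioid dose is simply not stated.

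**Conclusion.** The concern holds as a gap with a foreseeable consequence. Collection ends with the PICU stay in both groups, stay varies, and no rule covers days after transfer. Comparisons after about POD 2 are therefore, by clear implication, among children still in the PICU and at risk of selection bias. Neither direction nor size can be derived from the documents. The illustrative 5% to 10% on POD 4 to 7 rests on the assumed stay distribution, a correlation of 0.5 and a one-day difference. It is a quarter to a half of the 20% effect used in 15.2, and it vanishes if stays are equal and there is no effect, or if discharge is unrelated to need.

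The first 48 hours should be little affected. The outcome is secondary, in a pilot with non-randomised controls. The change is worth making because this outcome exists to describe how the effect changes with time, which is the feature that discharge can distort.

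**What to change.** In 3.2, 15.1 and 15.3:

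- Read daily opioid doses from the same electronic record for every child in both groups over a common set of post-operative days, whether or not the child has left the PICU. The 7 days used in the 15.2 table are a natural choice. Prospective extraction would then have to wait until that window closes.
- State that a post-transfer day is never counted as zero by default.
- If ward doses will not be extracted, limit the between-group daily comparison to the 7am-to-7am days on which essentially all children in both groups are still in the PICU, and report later days descriptively. Section 4.1 suggests about the first 48 hours. This should be checked against the data, since POD 2 on the 7am clock can end more than 48 hours after surgery.
- Report the number of children contributing on each day, by group.
- Analyse the days jointly in a mixed model with group, day, group-by-day and the 15.3 covariates (transplant type, age, gender).

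The cost is a few more days of medication-record extraction per child, or fewer days in the between-group comparison, plus one more model. Fixing a window for the primary total would not repair the daily means unless post-transfer doses are also collected.
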